### **8.4 Statistical Analysis Process**

The study will be analyzed by the Sponsor (or a nominated designee).

The primary endpoint (proportion who have died or progressed to RF at Day 28) will be analyzed using a logistic regression with treatment group and covariates, age group (50 to <75 years, and > 75 years), baseline WHO ordinal clinical scale (3 or 4), and region. Other covariates including previous COVID-19 therapy may be explored. Estimation of the covariate-

adjusted difference in proportion responding will be reported using Cochran-Mantel-Haenszel (CMH) weighting and estimates from the logistic regression (LR) as described by Ge and colleagues (Ge et al., 2011, Appendix C). This analysis will be repeated without the covariate. Deaths prior to Day 28 will be included in the endpoint (RF, death). WHO Ordinal Scale for COVID-19 scores ([Table 2](#)) will be analyzed by carrying forward any early deaths through Day 28; other categorical and continuous outcomes will be described. The primary analysis will be based on the Intent-to-Treat population (ITT), analyzed as randomized. The denominator for the proportions alive and RF-free at Day 28 will include all randomized subjects. Subjects lacking sufficient data to confirm RF-free and alive at Day 28 will be included in the primary analysis as treatment failures. If more than 5% of subjects have insufficient data to confirm RF-free and alive at Day 28, BioAge will employ a MI strategy (SAS MI, MIANALYZE) based on the patients last known status. For example, the last known WHO Score for a patient lost to follow-up can be used to impute missing primary outcome from patients with known primary outcome and similar WHO Scores. For the primary comparison, analysis by treatment group will be, “as randomized”. Secondary analyses of the primary endpoint may be repeated for the mITT and the per protocol populations, analyzed as treated. Time-to-RF will be analyzed using methods of Kaplan-Meier (KM), with time zero at randomization. Hazard ratios (Cox PHREG) with 95% confidence intervals will describe the treatment effect.

A sensitivity analysis may be completed to assess concurrent treatments and prior SARS-CoV-2 vaccinations in relation to the primary endpoint.

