4.0	14MAR2022	[REDACTED]	Updated per FDA comments dated November 24, 2021 and BioAge response.
5.0	01JUN2022	[REDACTED]	
1. Update on primary endpoint analysis by removing baseline WHO ordinal scale/ Addendum is added for the justification.2. Other minor corrections

1 Introduction

This Statistical Analysis Plan (SAP) contains a more technical and detailed elaboration of the principal features of the analysis described in the protocol and includes detailed procedures for executing the statistical analysis. This SAP should be used in conjunction with the protocol. If there are any discrepancies between the protocol and SAP, this SAP will prevail. Any deviations from this SAP that are implemented in the final analysis will be documented with sound clinical and statistical rationale in the Clinical Study Report (CSR). In the event of any changes to the primary endpoints or analyses, these changes will be documented through a protocol amendment, consistent with ICH E9 Statistical Principles for Clinical Trials.

The SAP is based on protocol v5.0, Amendment 04 dated 07 Sep 2021.

Pharmacokinetics (PK) and pharmacodynamics (PD) analyses and reporting are not included in this analysis plan.

A separate document contains the table, figure and listing specifications and any example programming codes.

2 Study Design

This is a randomized, placebo-controlled, parallel-group, multicenter, double-blind study of asapiprant (BGE-175) administered by oral administration (PO) or through a nasogastric tube (NG) in patients \geq 50 years of age and hospitalized with documented coronavirus disease 2019 (COVID-19) infection who are not yet in respiratory failure (RF).

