10.1 Primary efficacy analysis

The number and percentage of patients who have died or have progressed to RF through Day 28 will be presented by treatment. Hypothesis test comparison of proportion between treatment will be analyzed using a logistic regression with predefined covariates and treatment group. The predefined covariates are region and age group. Other covariates including previous COVID-19 therapy may be explored as exploratory analyses. Estimation of the covariate-adjusted risk difference will be reported using Cochran-Mantel-Haenszel (CMH) weighting and estimates from the logistic regression as described by Ge and colleagues (Ge et al., 2011, Appendix C). Two-sided p-value of global test comparison between active and placebo will be reported. Odds ratio of each covariate and two-sided 95% CI will also be reported. This analysis will be repeated without the covariates.

The denominator for the proportions alive and RF-free at Day 28 will include all randomized subjects.

Time from date of randomization to death or first RF through Day 28, whichever comes first, will also be displayed using the Kaplan-Meier estimator and analyzed using a proportional hazards model analysis with the same covariates. If a patient doesn't have documented death or RF, it will be censored at the Day 28. For subject who discontinued study before Day 28 without documented outcome, it will be censored at the date of discontinuation. This analysis will be repeated without the covariates. Test statistics will be the Hazard Ratio with 95% CIs and p-values. Sensitivity test will be done using a Fishers Exact Test.

Primary endpoint will be analyzed using ITT, mITT, PPS (if formed) analysis set under randomized treatment.

Primary endpoint analysis will be repeated for subgroups as specified [section 4.3](#).

Sensitivity analysis and handling of missing primary endpoint data

If $\leq 5\%$ of subjects lack sufficient data to confirm the primary endpoint, four sensitivity analyses will be performed on logistic regression: 1) treat any missing primary outcomes as successes; 2) replaces

QMS Document Name: Statistical Analysis Plan	Page 18 of 27
QMS No (include version ref): STF-015-GL.02	Document date: 09JUL2019
CONFIDENTIAL	

any missing primary outcomes as failures; 3) missing primary outcome imputed as success for drug and failure for controls; 4) missing primary outcome imputed as failure for drug and success for controls.

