at the IA of between $Z=1.41$ and 2.21 would define the promising zone and opportunity for BioAge to expand the study. For example, if at IA, $Z=1.8$ ($CP=0.66$), then to maintain the power at 0.90 the study could be expanded from 312 subjects to 500. For results in the Mehta and Pocock unfavorable zone, or in the favorable zone, the study will continue to conclusion at $N=312$ subjects.

14 Statistical Analyses for Safety Monitoring

The statistical analysis for safety monitoring is specified in a separate DMC charter.

15 References

1. Guideline on adjustment for baseline covariates in clinical trials, EMA/CHMP/295050/2013, 2015
3. Senn SJ. Covariate imbalance and random allocation in clinical trials. *Stat Med* 1989;8:467e75.
4. ICH Harmonised Tripartite Guideline E9, Statistical Principles for Clinical Trials, 1998
5. ICH Harmonised Tripartite Guideline E3, Structure and Content of Clinical Study Reports. 1996
6. ICH Harmonised Tripartite Guideline E6(R2), Guideline for Good Clinical Practice, 2018
7. ICH guideline E2F, Note for guidance on development safety update reports, EMA/CHMP/ICH/309348/2008, September 2010
8. Guideline on missing data in confirmatory clinical trials, EMA/CPMP/EWP/1776/99 Rev. 1, 2010
9. ICH E9 (R1) addendum on estimands and sensitivity analysis in clinical trials to the guideline on statistical 6 principles for clinical trials, Step 2b (Draft), EMA/CHMP/ICH/436221/2017, 2017
10. Mehta, C.R., and Pocock, S.J. (2011) Adaptive increase in sample size when interim results are promising: a practical guide with examples. *Stat Med* 40, 3267–3284.

QMS Document Name: Statistical Analysis Plan	Page 26 of 27
QMS No (include version ref): STF-015-GL.02	Document date: 09JUL2019
CONFIDENTIAL	

16 Addendum

Based on the following information and justifications, baseline WHO ordinal scale is removed from primary endpoint logistic regression:

- 1) enrollment stopped before interim analysis and all enrolled patients have passed Day 28;

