- 2) based blinded data review, all those subjects who had baseline WHO scale=3 had no respiratory failure, and therefore leading quasi-complete separation on primary endpoint.

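### SAP v5.0 drops baseline WHO score from the primary model because of separation, but separation leaves the treatment effect estimable; a named WHO-adjusted analysis should stand beside the reduced model and the change be recorded by protocol amendment

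*SAP*

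**What the plan says.** Protocol 8.4 specifies a logistic regression for death or respiratory failure by Day 28, with treatment, age group, "baseline WHO ordinal clinical scale (3 or 4), and region". SAP 10.1 now reads: "The predefined covariates are region and age group". The SAP modification history lists the removal as a v5.0 change and points to the section 16 addendum, which gives two reasons. The first is that "enrollment stopped before interim analysis and all enrolled patients have passed Day 28". The second is that, on blinded review, "all those subjects who had baseline WHO scale=3 had no respiratory failure, and therefore leading quasi-complete separation on primary endpoint".

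On the effect measure, SAP 10.1 says: "Estimation of the covariate-adjusted risk difference will be reported using Cochran-Mantel-Haenszel (CMH) weighting and estimates from the logistic regression". It also asks for an odds ratio and 95% confidence interval for each covariate.

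On precedence, SAP section 1 states: "If there are any discrepancies between the protocol and SAP, this SAP will prevail". It adds: "In the event of any changes to the primary endpoints or analyses, these changes will be documented through a protocol amendment". It also states: "The SAP is based on protocol v5.0, Amendment 04 dated 07 Sep 2021". That is the protocol version that still lists the WHO covariate.

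Baseline WHO remains an exploratory subgroup factor (SAP 4.3) and a covariate for the continuous endpoints in 10.2.4. The 10.2.3 ANCOVA on change in WHO score names only the stratification factors.

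**The concern.** The first addendum reason concerns timing. Separation is the only statistical reason given for dropping the covariate, and it does not affect the treatment term. A baseline score on which one level had no respiratory failure is strongly prognostic, and it is already collected.

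The trial also appears to have stopped short. The interim was due at about 208 subjects through Day 28. Enrolment stopped before it and everyone has passed Day 28, which suggests a final N at or below about 208 rather than 312, although the number is not stated. In a smaller trial, precision from a baseline covariate is worth more, and an uneven split of WHO=3 subjects between arms passes directly into an unadjusted estimate.

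**Working it through.** **Inputs.** From the documents: 31% vs 15%, two-sided 5%, 90% power, 1:1, N=312 (Protocol 8.6), and an interim at about 208 (SAP 13). Assumed because not disclosed: WHO=3 share s of 5, 10, 20 or 30%; final N of 100 to 312; zero true WHO=3 risk; and, in the simulations, age and region prevalence and effects.

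**1. The plan's own figure.** With mean rate 0.23, n per arm = [1.96√(2·0.23·0.77) + 1.2816√(0.31·0.69 + 0.15·0.85)]² / 0.16² = 143.3. The continuity correction (n/4)[1 + √(1 + 4/(0.16n))]² gives 155.5, so 156 per arm and 312 in total. Exact Fisher power at 156 per arm is 90.5%. The stated N reproduces.

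**2. What separation does.** With no events at WHO=3, the WHO coefficient runs to minus infinity. The WHO=3 likelihood contribution then tends to 1 whatever the treatment coefficient, so what remains is the WHO=4 likelihood. In a worked example the WHO coefficient went from -5.3 (SE 2.7) to -30.3 (SE about 726,000) as iterations continued. The treatment log-odds ratio settled at -0.9935 (SE 0.2940), identical to the fit on WHO=4 alone. The standardised risk difference was finite: -0.159 (SE 0.045), against -0.179 (SE 0.047) unadjusted. Over 2,000 simulated trials the with-WHO and WHO=4-only treatment results differed by less than 1e-9.

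**3. Power, same estimator and test.** By step 2, keeping WHO equals analysing N(1-s) subjects at rates 0.31/(1-s) and 0.15/(1-s). Power = Φ(d/SE - 1.96), where d is the log-odds ratio and SE² = 1/(n·p1·q1) + 1/(n·p2·q2).

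Example, N=208, s=20%:
- Without WHO: n=104, d=0.9345, SE=0.3469, ratio 2.694, power 76.8%.
- With WHO: n=83.2, rates 0.3875 and 0.1875, d=1.0085, SE=0.3599, ratio 2.802, power 80.0%.
- Gain: 3.2 points.

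| N | Power without WHO (%) | Gain, s=5% | 10% | 20% | 30% |
|---|---|---|---|---|---|
| 100 | 46.3 | 0.6 | 1.3 | 3.0 | 5.4 |
| 132 | 57.4 | 0.7 | 1.5 | 3.4 | 5.9 |
| 208 | 76.8 | 0.7 | 1.4 | 3.2 | 5.5 |
| 312 | 91.0 | 0.4 | 0.9 | 2.0 | 3.3 |

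Simulation with age and region in the model (12,000 trials per setting) gave these Wald gains at the same four shares:
- N=132: 0.7, 1.5, 3.5, 6.3.
- N=200: 1.0, 1.8, 2.8, 5.4.
- N=312: 0.4, 0.8, 1.7, 2.6.

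Likelihood-ratio gains were within 0.4 point of these. Type I error was 5.0-5.4% with and without WHO.

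**4. Where the gain is smaller.**
- If 31%/15% are the WHO=4 rates rather than the overall rates, shares of 20-30% give 1.8-3.8 points for N of 100-312.
- If true WHO=3 risk is a quarter of WHO=4 risk and no WHO=3 event is seen, Firth with WHO against the current Wald test at N=200 gains 0.3, 0.9 and 1.8 points at 5, 10 and 20%. The chance of seeing zero WHO=3 events is then 0.55, 0.29 and 0.07.
- Firth with WHO against the current model's likelihood-ratio test gives -0.5, +0.6, +2.4, +4.7 points at N=200 and -1.4, -0.3, +2.1, +4.5 at N=132.

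**5. Chance imbalance, N=200, no treatment effect.** One standard deviation of the between-arm difference in WHO=3 share is √(4s(1-s)/N). Multiplied by the WHO=4 risk, 0.23/(1-s), this shifts the risk difference by 0.75, 1.1, 1.6 and 2.1 points at the four shares. The standard error is √(4·0.23·0.77/200), about 6 points.

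**The case against.** The strongest reply is that nothing here is an error. Randomisation makes the reduced model valid, the choice was made on blinded data, and the SAP says which document governs. Dropping WHO also has practical merits. Every randomised subject contributes to the odds ratio, the existing logistic and imputation code runs unchanged, and every required covariate odds ratio is finite. Sensitivity analyses that impute missing outcomes as failures cannot switch separation on and off between runs. The WHO=4 subgroup output already contains the ML-adjusted treatment odds ratio. All of that stands, and it is why the reduced model may remain primary. It does not show that separation forces removal, and an exploratory subgroup is not a named adjusted analysis of all randomised subjects.

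Four stronger readings are not supported:
- **The reduced model is biased, or was chosen to favour the drug.** The addendum describes blinded review, and type I error is about 5% either way.
- **Three to six points are being lost.** That needs a WHO=3 share of 20-30%, N of about 100-208 and no WHO=3 risk. If WHO=3 risk is not nil, seeing zero events points towards a small WHO=3 group, where the gain is near nil.
- **The primary model is unclear because the documents differ.** SAP section 1 settles precedence.
- **No amendment was made.** The documents supplied show none after v5.0 but cannot exclude a later one.

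**Conclusion.** Separation is a real obstacle to reporting a WHO odds ratio, but not to adjusting the treatment comparison for WHO. The cost of dropping WHO is modest and depends on figures the plan does not disclose: about 0-2 power points at a 5-10% WHO=3 share, and at 20-30% about 3-6 points for N of about 100-208 or about 2-3 at N=312. These rest on 31%/15% overall, zero true WHO=3 risk, and like-for-like estimation and testing.

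Three points do not depend on the share:
- SAP section 1 calls for a protocol amendment, and the SAP still cites the version that lists the covariate.
- The addendum mentions only respiratory failure, while the endpoint also counts death, and Protocol 8.4 counts unconfirmed outcomes as failures. Its reference to the primary endpoint may be meant to cover deaths, but a single such WHO=3 failure would remove the separation, so the counts matter.
- The 10.2.3 model for change in WHO score omits the baseline score that 10.2.4 includes.

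**What to change.** Before unblinding:

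1. Pre-specify a named analysis of the primary endpoint in all randomised subjects, adjusted for region, age group and baseline WHO (3 vs 4), beside the current model. Use either ordinary logistic regression with a likelihood-ratio test and the WHO odds ratio reported as not estimable, or Firth's penalised likelihood. Report the standardised risk difference with it. Whether this becomes the primary model is the sponsor's choice.
2. Add baseline WHO score as a covariate in the 10.2.3 ANCOVA.
3. Record the primary-model change by protocol amendment. State the number of WHO=3 subjects and confirm that none died or had an unconfirmed Day 28 outcome.

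No new data are needed. The cost is SAP text, a model option, the amendment, and imputation and pooling code that can handle the WHO term if more than 5% of outcomes are missing. The downsides are that the WHO odds ratio is not interpretable and the treatment odds ratio becomes conditional on WHO. With Firth, standardised arm risks run 0.4-1.1 points high, although the risk difference moves by 0.2 points or less. If WHO=3 is rare, the gain is negligible.
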